7.8.4 Statistical/Analytical Issues

7.8.4.1 Adjustments for Covariates

Not applicable.

CONFIDENTIAL

7.8.4.2 *Handling of Dropouts or Missing Data*

Missing test results and data determined to be non-evaluable according to this SAP will not be used for hypothesis testing and estimations. For the analysis of the SRH antibody titer, values below the lower reporting limit will be replaced with 4, whereas those above the upper reporting limit will be replaced with the upper reporting limit¹. For the analysis of the MN antibody titer, values below the lower reporting limit will be replaced with 7.1, whereas those above the upper reporting limit will be replaced with the upper reporting limit.

7.8.4.3 *Multicenter Studies*

Since this is a single-arm study, treatment-by-site interaction will not be evaluated.

7.8.4.4 *Multiple Comparison/Multiplicity*

Not applicable.

7.8.4.5 *Use of an "Efficacy Subset" of Subjects*

Not applicable.

7.8.4.6 *Active-Control Studies Intended to Show Equivalence or Non-Inferiority*

Not applicable.

7.8.4.7 *Examination of Subgroups*

Not applicable.

7.9 **Pharmacokinetic/Pharmacodynamic Analysis**

7.9.1 **Pharmacokinetic Analysis**

Not applicable.

7.9.2 **Pharmacodynamic Analysis**

Not applicable.

7.10 **Other Outcomes**

Not applicable.

¹ Note for guidance on harmonisation of requirements for influenza vaccines(CPMP/BWP/214/96)

7.11 Safety Analysis

7.11.1 Adverse Events

7.11.1.1 Overview of Treatment-Emergent Adverse Events

Analysis set: Safety analysis set

Analysis variable(s): TEAE

Categories: Relationship to study drug [Related, Not related]

Intensity [Mild, Moderate, Severe]

Analysis methods: The following summaries will be provided on the above variables.

(1) Overview of TEAEs

- 1) All TEAEs (number of events, number and percentage of subjects)
- 2) Relationship of TEAEs to study drug (number of events, number and percentage of subjects)
- 3) Intensity of TEAEs (number of events, number and percentage of subjects)
- 4) TEAEs leading to study drug discontinuation (number of events, number and percentage of subjects)
- 5) Serious TEAEs (number of events, number and percentage of subjects)
- 6) Relationship of serious TEAEs to study drug (number of events, number and percentage of subjects)
- 7) Serious TEAEs leading to study drug discontinuation (number of events, number and percentage of subjects)
- 8) TEAEs resulting in death (number of events, number and percentage of subjects)

TEAEs will be counted according to the rules below.

[Number of subjects]

- Summaries for 2) and 6)
A subject with occurrences of TEAE in both categories (i.e., “Related” and “Not related”) will be counted once in the “Related” category.
- Summary for 3)
A subject with multiple occurrences of TEAE will be counted once for

the TEAE with maximum intensity.

- Summaries other than 2), 3), and 6)
A subject with multiple occurrences of TEAE will be counted only once.
[Number of events]
For each summary, the total number of events will be calculated.

7.11.1.2 Displays of Treatment-Emergent Adverse events

Analysis set: Safety analysis set

Analysis variable(s): TEAE

Categories: Intensity [Mild, Moderate, Severe]
Vaccination number [Initial vaccination, Second vaccination]
Timing of onset by vaccination number [Day 1 of the initial vaccination \leq - \leq Day 7 of the initial vaccination, Day 8 of the initial vaccination \leq - \leq Before the second vaccination]
[Day 1 of the second vaccination \leq - \leq Day 7 of the second vaccination, Day 8 of the second vaccination \leq - \leq Max]

Analysis methods: The following summaries will be provided for the above analysis variables using frequency tabulations.

TEAEs will be coded using the MedDRA and summarized by SOC and PT. SOC will be sorted alphabetically and PT in decreasing frequency for tables provided by SOC and PT. SOC and PT will be sorted in decreasing frequency for tables provided by SOC only or PT only.

- (1) TEAEs by SOC and PT
- (2) TEAEs by SOC
- (3) TEAEs by PT
- (4) Drug-related TEAEs by SOC and PT
- (5) Intensity of TEAEs by SOC and PT
- (6) Intensity of drug-related TEAEs by SOC and PT
- (7) TEAEs leading to study drug discontinuation by SOC and PT
- (8) Serious TEAEs by SOC and PT

(9) Vaccination number of TEAEs by SOC and PT
(10) Vaccination number and timing of onset of TEAEs by SOC and PT

For each frequency tabulation, the number and percentage of subjects will be obtained according to the rules below.

[Number of subjects]

- Summaries other than (5), (6), (9), and (10)
A subject with multiple occurrences of TEAE within a SOC will be counted only once in that SOC. A subject with multiple occurrences of TEAE within a PT will be counted only once in that PT. The percentage of subjects with TEAEs will be calculated using the number of subjects in the safety analysis set as the denominator.
- Summaries for (5) and (6)
A subject with multiple occurrences of TEAE within a SOC or a PT will be counted only once for the TEAE with maximum intensity in that SOC or PT. The percentage of subjects with TEAEs will be calculated using the number of subjects in the safety analysis set as the denominator.
- Summary for (9)
A subject with multiple occurrences of TEAE within a SOC or a PT will be counted once in each relevant category of vaccination number. For calculation of the percentage of subjects with TEAEs for each vaccination number, the denominator used will be the number of subjects “who received the study drug of the relevant vaccination number” in the safety analysis set.
- Summary for (10)
A subject with multiple occurrences of TEAE within a SOC or a PT will be counted once in each relevant category of vaccination number and timing of onset. For calculation of the percentage of subjects with TEAEs for each timing of onset, the denominator used will be the number of subjects “who received the study drug of the relevant vaccination number” in the safety analysis set.

7.11.1.3 Displays of Pretreatment Events

Analysis set: All subjects who signed the informed consent form

Analysis variable(s): PTE

Analysis methods: The following summaries will be provided for the above analysis variables using frequency tabulations.

CONFIDENTIAL

PTEs will be coded using the MedDRA and summarized by SOC and PT. SOC will be sorted alphabetically and PT in decreasing frequency.

- (1) PTEs by SOC and PT
- (2) Serious PTEs by SOC and PT

Frequency tabulation will be provided according to the rules below.

[Number of subjects]

A subject with multiple occurrences of PTE within a SOC will be counted only once in that SOC. A subject with multiple occurrences of PTE within a PT will be counted only once in that PT.

[Number of events]

For each summary, the total number of events will be calculated.

7.11.1.4 Displays of Solicited Local and Systemic Adverse Events

Analysis set: Safety analysis set

Analysis variable(s): Solicited local and systemic AEs to be recorded in the subject diary

Categories: Intensity [Mild, Moderate, Severe]

Vaccination number [Initial vaccination, Second vaccination]

Timing of onset by vaccination number [Day 1 of the initial vaccination \leq - \leq Day 7 of the initial vaccination, Day 8 of the initial vaccination \leq - \leq Before the second vaccination]

[Day 1 of the second vaccination \leq - \leq Day 7 of the second vaccination, Day 8 of the second vaccination \leq - \leq Max]

Analysis methods: The following summaries will be provided for the above analysis variables using frequency tabulations.

- (1) Solicited local and systemic AEs recorded in the subject diary
- (2) Solicited local and systemic AEs recorded in the subject diary by intensity
- (3) Solicited local and systemic AEs recorded in the subject diary by vaccination number
- (4) Solicited local and systemic AEs recorded in the subject diary by vaccination number and timing of onset

For each frequency tabulation, the number and percentage of subjects will be obtained according to the rules below.

[Number of subjects]

- Summary for (1)
A subject with multiple occurrences of a solicited local or systemic AE recorded in the subject diary will be counted only once for that AE. The percentage of subjects with solicited local or systemic AEs recorded in the subject diary will be calculated using the number of subjects in the safety analysis set as the denominator.
- Summary for (2)
A subject with multiple occurrences of a solicited local or systemic AE recorded in the subject diary will be counted only once for the AE with maximum intensity. The percentage of subjects with solicited local or systemic AEs recorded in the subject diary will be calculated using the number of subjects in the safety analysis set as the denominator.
- Summary for (3)
A subject with multiple occurrences of a solicited local or systemic AE recorded in the subject diary will be counted once in each relevant category of vaccination number. For calculation of the percentage of subjects with solicited local or systemic AEs recorded in the subject diary for each vaccination number, the denominator used will be the number of subjects “who received the study drug of the relevant vaccination number” in the safety analysis set.
- Summary for (4)
A subject with multiple occurrences of a solicited local or systemic AE recorded in the subject diary will be counted once in each relevant category of vaccination number and timing of onset. For calculation of the percentage of subjects with solicited local or systemic AEs recorded in the subject diary for each timing of onset, the denominator used will be

CONFIDENTIAL

the number of subjects “who received the study drug of the relevant vaccination number” in the safety analysis set.

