Form Days 29 to 43 (before visiting the study site), subjects will measure their body temperature (oral) only if they develop pyrexia (or any symptoms suggestive of pyrexia) (see Section 9.1.11).
- Supply of the subject diary
 - Time point: Day 22 (Diaries 3 and 4) (Diaries 3 and 4 may be supplied on Day 1)
- Completion of the subject diary (by subjects)
 - Time point: From Day 22 (after vaccination) to Day 28 (Diary 3) and from Day 29 to Day 43 (before visiting the study site) (Diary 4)

During the periods from Day 22 (after the completion of study visit) to Day 28 and from Day 29 to Day 43 (before visiting the study site), subjects will monitor for and record any systemic reactions, injection site reactions, etc. (see Section 9.1.11).

9.3.5 <Treatment Period/at the End of Study/Day 43>

The following testing, observation, and assessments will be performed at the final study visit (for observation) (Day 43).

CONFIDENTIAL

- Physical Examination
- Vital signs (body temperature [oral], blood pressure, and pulse rate)
- Pregnancy test (only for female subjects of childbearing potential)
- Blood sampling for the immunogenicity evaluation
- Collection of the subject diary (Diaries 3 and 4)
- Collection of concomitant medications and AEs

For all subjects receiving the study drug, the investigator must complete the Subject Status (e)CRF page.

9.3.6 <Treatment Period/at Discontinuation>

For subjects withdrawn from the study, reasons for study discontinuation must be recorded in the subject's source documents and CRF, and the following testing, observation, and assessments should be performed wherever possible.

- Physical Examination
- Vital signs (body temperature [oral], blood pressure, and pulse rate)
- Pregnancy test (only for female subjects of childbearing potential)
- Blood sampling for the immunogenicity evaluation
- Collection of the subject diary
- Collection of concomitant medications and AEs

For all subjects receiving the study drug, the investigator must complete the Subject Status (e)CRF page.

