6.0 DETERMINATION OF SAMPLE SIZE

Number of subjects to be vaccinated: 55

The objective of this study is to evaluate the immunogenicity and safety of two intramuscular vaccinations with BLB-750 in healthy Japanese adults. Therefore, the sample size for this study was determined to be 55 subjects, as the number of subjects to be vaccinated, by reference to the Notification issued by the Director of the Evaluation and Licensing Division of the Pharmaceutical and Food Safety Bureau on October 31, 2011: “Guidelines for the Development of Prototype Vaccines in Preparedness for Pandemic Influenza” [1]. There are no statistical rationales for the determination of this sample size.

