7.2 Analysis Sets

- Full analysis set (FAS): All subjects who received at least one dose of the study drug.
- Safety analysis set: All subjects who received at least one dose of the study drug.

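### Solicited-reaction percentages divide by every recipient, so a recipient with no diary data and no later contact counts as reaction-free

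*SAP*

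**What the plan says.** SAP 7.11.1.4 plans four summaries of solicited local and systemic reactions: (1) overall, (2) by intensity, (3) by vaccination, and (4) by vaccination and timing of onset.

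- For (1) and (2), the percentage of subjects with reactions "recorded in the subject diary will be calculated using the number of subjects in the safety analysis set as the denominator". SAP 7.2 defines that set without any condition on post-vaccination data: "Safety analysis set: All subjects who received at least one dose of the study drug".
- For (3) and (4), the denominator is the subjects "who received the study drug of the relevant vaccination number". Summary (4) applies this to each onset period: "For calculation of the percentage of subjects with solicited local or systemic AEs recorded in the subject diary for each timing of onset".

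The numerator comes from the diaries. Under Protocol 9.1.11 the investigator reads them when they are collected, Diaries 1 and 2 at Day 22 and Diaries 3 and 4 at Day 43. Appendix A gives a second chance to collect Diaries 1 and 2 at the last visit. For subjects who discontinue, Protocol 9.3.6 lists diary collection among items for which "the following testing, observation, and assessments should be performed wherever possible". Protocol 7.5 foresees loss to follow-up after failed contact, and Protocol 7.6 does not replace vaccinated subjects who withdraw.

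The SAP has no rule for an unreturned or incomplete diary. Its one rule on missing results, in SAP 7.8.4.2, sits in the efficacy section: "Missing test results and data determined to be non-evaluable according to this SAP will not be used for hypothesis testing and estimations".

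**The concern.** The tables cannot separate a subject who had no reaction from one about whom nothing is known. Both add one to the denominator and nothing to the numerator.

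This matters more here than in a controlled trial. Protocol 6.2.1 describes the study as uncontrolled, so no comparator arm shares the bias, and the absolute percentages are the safety result. Solicited reactions come first among the safety endpoints in SAP 5.0. Protocol 4.2 says there is no clinical experience with a vaccine made from an attenuated strain. An error that can only lower the reported reaction rates deserves a guard, even if it is likely to be small.

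**Working it through.** **No planned rate to reproduce.** The only figure the plan gives is the size: "Number of subjects to be vaccinated: 55". SAP 6.0 adds: "There are no statistical rationales for the determination of this sample size". No reaction rate, dropout rate or diary-return rate is stated.

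**Inputs.** n is the number who received the dose; 55 is planned for dose 1. m is the number of those with no diary data and no recorded solicited event (assumed 1, 3 or 5). x is the number of recipients with a recorded reaction.

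**Formulas for one dose.**
- SAP percentage: x/n.
- Percentage among recipients with data: x/(n − m).
- Ratio of the two: (n − m)/n, so the relative shortfall is m/n.
- Upper bound, if every recipient without data had reacted: (x + m)/n.

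Recorded reactors cannot outnumber true reactors, so x/n is never above the true proportion among all recipients.

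**Dose 1, n = 55, with about half of those with data reacting (assumed).**

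| m | Relative shortfall | SAP percentage | Among those with data | Upper bound |
|---|---|---|---|---|
| 0 | 0% | 28/55 = 50.9% | 28/55 = 50.9% | 50.9% |
| 1 | 1/55 = 1.8% | 27/55 = 49.1% | 27/54 = 50.0% | 28/55 = 50.9% |
| 3 | 3/55 = 5.5% | 26/55 = 47.3% | 26/52 = 50.0% | 29/55 = 52.7% |
| 5 | 5/55 = 9.1% | 25/55 = 45.5% | 25/50 = 50.0% | 30/55 = 54.5% |

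In percentage points, the expected shortfall is p × m/n if missing diaries are unrelated to reactions, where p is the reaction rate. At m = 3 it is 0.10 × 3/55 = 0.5 points for p = 10% and 0.70 × 3/55 = 3.8 points for p = 70%. For comparison, the exact 95% interval for 26/55 runs from 33.7% to 61.2%.

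**Dose 2 in (3) and (4).** A subject lost before dose 2 is not in this denominator and has no effect. Suppose three are lost before dose 2, so n = 55 − 3 = 52. If all 52 return dose-2 diaries, the shortfall is nil. If two of the 52 do not, it is 2/52 = 3.8%.

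**Summaries (1) and (2).** The full loss falls only on subjects with no diary at all, mainly those who disappear before Day 22. A subject with dose-1 diaries but no dose-2 diaries is wrongly counted in (1) only if the reaction would have appeared after dose 2 and not after dose 1. In (2) the maximum intensity can also be missed.

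**Onset from Day 8.** In (4), a recipient who leaves before Day 8 stays in the denominator for the later period without having been observed in it.

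**The case against.** The strongest reply is that this is a deliberate convention. SAP 7.11.1.2 uses the same denominators for TEAEs generally, and Protocol 13.1.4 assigns solicited events to the safety analysis set. The study has one site, 55 healthy adults and three visits in 43 days, so few diaries may go missing. Several provisions reduce the loss:

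- Efforts to complete early-termination procedures (Protocol 7.6).
- Documented contact attempts (Protocol 7.5).
- Observation for at least 30 minutes after each dose (Protocol 9.2).
- AE reporting at any time (Protocol 10.2.1.2).

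The daily number of subjects in the body-temperature summaries (SAP 7.11.3) also gives a rough view of diary return. The tables are descriptive, with no threshold attached.

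Most of this stands as a limit on size. It does not remove the bias: none of these provisions reaches a subject who never returns and makes no contact, and the temperature counts appear in a different table. The convention is a good reason to keep the all-vaccinated percentage, but not to make it the only one.

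A reader might infer three stronger things that the documents do not support.

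- That reactogenicity is in fact understated. This happens only if diaries are missing, and no rate is given.
- That every solicited percentage is low by m/55. The dose-2 rows and the pooled summaries behave differently, as shown above.
- That the SAP contradicts itself because missing titers are left out while missing diaries are not. A titer is a measurement under an efficacy rule, and AE incidence follows another convention. The contrast shows that a rule for diaries is lacking; it is not an inconsistency in itself.

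**Conclusion.** The point holds as a conditional, one-directional bias built into a stated rule. Any recipient without diary data or later contact is scored as reaction-free. For the dose concerned, the reported rate is (n − m)/n of the rate among recipients with data: for dose 1 with n = 55, low by 1.8%, 5.5% or 9.1% in relative terms for m = 1, 3 or 5. With m up to 3 the shift lies well inside the sampling uncertainty.

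The size rests on an assumed m. The comparison with recipients who have data equals the expected bias only if missing diaries are unrelated to reactions. If non-returners reacted more often the bias is larger, and if less often it is smaller, but it never reverses. The documents do not say which is more likely.

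**What to change.** In SAP 7.11.1.4, for each vaccination:

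1. Calculate the main percentage among recipients of that dose with at least one post-dose diary record in the eCRF or a recorded solicited AE. A transcribed Day 1–7 or Day 22–28 temperature would serve, since Protocol 9.1.11 has these transcribed even when below 38.0°C.
2. For onset from Day 8, use recipients with follow-up beyond Day 7, shown by a diary or a later visit. Diaries 2 and 4 need no daily entry, so a blank one should not be read as missing when the subject attended afterwards.
3. For (1) and (2), which pool the doses, require data after at least one dose, and show how many subjects lack data for a dose they received.
4. Show the number vaccinated but without data in each table.
5. Keep the all-vaccinated percentage as a supportive figure, so that solicited events can be matched to the TEAE tables in SAP 7.11.1.2, which stay as they are.

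The cost is a few sentences in the SAP, a second percentage and a count per table, and slightly higher main percentages if any diaries are missing. The diary condition can be built from temperatures already in the eCRF.

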7.11.2 Clinical Laboratory Evaluations

Not applicable.

7.11.3 Vital Signs

Analysis set: Safety analysis set

Analysis variable(s): Systolic blood pressure
Diastolic blood pressure

Pulse rate

Body temperature

Respiratory rate

Assessment point: Systolic blood pressure, diastolic blood pressure, pulse rate: Prevaccination, 30 minutes after the initial vaccination, Day 22 of the initial vaccination (before the second vaccination), 30 minutes after the second vaccination, Day 22 of the second vaccination

Body temperature: Prevaccination; Days 1 (after vaccination), 2, 3, 4, 5, 6, 7, and 22 (before the second vaccination) of the initial vaccination; Days 1 (after vaccination), 2, 3, 4, 5, 6, 7, and 22 of the second vaccination

Respiratory rate: Prevaccination, 30 minutes after the initial vaccination, Day 22 of the initial vaccination (before the second vaccination), 30 minutes after the second vaccination

Analysis methods: For systolic/diastolic blood pressure, pulse rate and respiratory rate, analyses (1) and (3) below will be performed. For body temperature, analyses (2) and (3) below will be performed.

- (1) Summary statistics of measurement values and the changes in postvaccination values (postvaccination – prevaccination of each vaccination) at each assessment point
- (2) Summary statistics for measurement values at each assessment point
- (3) Case plots

7.11.4 12-Lead ECGs

Not applicable.

CONFIDENTIAL

7.11.5 Other Observations Related to Safety

7.11.5.1 Summary of the Longest Diameter of Local Reactions

Analysis set:	Safety analysis set	
Analysis variable(s):	Maximum diameter (cm) of injection site reaction	[Min≤ - <2.5, 2.5≤ - <5.1, 5.1≤ - <10.1, 10.1≤ - ≤Max]
	Maximum diameter (cm) of injection site swelling	[Min≤ - <2.5, 2.5≤ - <5.1, 5.1≤ - <10.1, 10.1≤ - ≤Max]
	Maximum diameter (cm) of injection site induration	[Min≤ - <2.5, 2.5≤ - <5.1, 5.1≤ - <10.1, 10.1≤ - ≤Max]
Categories:	Vaccination number	[Initial vaccination, Second vaccination]
Analysis methods:	
The following analyses will be performed on the above variables for each vaccination number.
 
(1) Frequency tabulations for categorical variables and summary statistics for continuous variables
	

7.11.5.2 Displays of Treatment-Emergent Adverse Events (Japanese)

Analysis set:	Safety analysis set
Analysis variable(s):	TEAE
Analysis methods:	TEAEs will be summarized in the same way as in Section 7.11.1.2. All summaries will be presented in Japanese.

7.12 Interim Analysis

No interim analysis is planned.

7.13 Changes in the Statistical Analysis Plan

Statistical Analysis Plan (Version 1: Created 7 May 2018 → Version 2: Created 3 Jul 2018)

Before change

Section 7.7: Study Drug Exposure and Compliance

Analysis variable(s): Time (days) from the initial vaccination to blood collection for antibody titer determination after the initial vaccination

[Min≤ - <22, 22≤ - <24, 24≤ - ≤Max]

CONFIDENTIAL

Time (days) from the second vaccination to blood collection for antibody titer determination after the second vaccination

[Min \leq - <20, 20 \leq - <24, 24 \leq - \leq Max]

Section 7.11.5.1: Summary of the Longest Diameter of Local Reactions

Analysis variable(s): Maximum diameter (cm) of injection site reaction

[Min \leq - <2.5, 2.5 \leq - <5.0, 5.0 \leq - <10.0, 10.0 \leq - \leq Max]

Maximum diameter (cm) of injection site swelling

[Min \leq - <2.5, 2.5 \leq - <5.0, 5.0 \leq - <10.0, 10.0 \leq - \leq Max]

Maximum diameter (cm) of injection site induration

[Min \leq - <2.5, 2.5 \leq - <5.0, 5.0 \leq - <10.0, 10.0 \leq - \leq Max]

After change

Section 7.7: Study Drug Exposure and Compliance

Analysis variable(s): Time (days) from the initial vaccination to blood collection for antibody titer determination after the initial vaccination

[Min \leq - <=21, 22 \leq - <=24, 25 \leq - \leq Max]

Time (days) from the second vaccination to blood collection for antibody titer determination after the second vaccination

[Min \leq - <=19, 20 \leq - <=24, 25 \leq - \leq Max]

Section 7.11.5.1: Summary of the Longest Diameter of Local Reactions

Analysis variable(s): Maximum diameter (cm) of injection site reaction

[Min \leq - <2.5, 2.5 \leq - <5.1, 5.1 \leq - <10.1, 10.1 \leq - \leq Max]

Maximum diameter (cm) of injection site swelling

[Min \leq - <2.5, 2.5 \leq - <5.1, 5.1 \leq - <10.1, 10.1 \leq - \leq Max]

Maximum diameter (cm) of injection site induration

[Min \leq - <2.5, 2.5 \leq - <5.1, 5.1 \leq - <10.1, 10.1 \leq - \leq Max]

Reason for change

Discrepancies from the protocol are corrected.

